3 DATA ANALYSIS CONSIDERATIONS

3.1 General presentation of summaries and analyses

Statistical evaluation will be performed by PAREXEL. The datasets will follow the UCB analysis data model (ADaM) specifications.

All analyses will be performed using SAS version 9.3 or higher (SAS Institute, Cary, North Carolina, United States of America). Continuous variables will be summarized by visit (where applicable) including number of subjects (n), arithmetic mean, SD, median, minimum and maximum. Categorical variables will be summarized by visit (where applicable) with frequency counts and percentages with 95% confidence intervals (CI) where stated. Geometric coefficient of variation (geoCV), geometric mean (geoMean) and 95% CI for the geoMean will also be presented in the descriptive statistics for the PK concentration data.

When reporting relative frequencies or other percentage values, the following rules apply:

- For values where all subjects fulfill certain criteria, the percentage value will be displayed as 100
- For values where the absolute frequency is zero, there will be no percentage displayed at all
- All other percentage displays will use 1 decimal place

Percentages displayed based on continuous data (eg, percentage changes from baseline) will be displayed to 1 decimal place.

When reporting descriptive statistics, the following rules will apply in general:

- n will be an integer
- Mean (arithmetic and geometric), SD and median will use 1 decimal place more than the original data
- Minimum and maximum will be reported using the same number of decimal places as the original value
- If no subjects have data at a given timepoint, for example, then only n=0 will be presented. If n<3, present the n, minimum and maximum only. If n=3, present the n, mean, median, minimum and maximum only. The other descriptive statistics will be left blank.

When reporting descriptive statistics for PK data, the following rules will apply with regard to rounding and precision:

- Individual values for PK concentration data will be reported to the same level of precision as received from the bioanalytical laboratory
- Descriptive statistics for PK concentration data will be reported to the same level of precision as the individual data for the minimum and maximum, and to 1 additional significant figure for the mean (arithmetic and geometric), median, SD and 95% CI for the geoMean
- Geometric CV will be reported as a percentage to 1 decimal place

All statistical tests will be carried out 1-tailed at the 5% level of significance unless otherwise stated. P-values will be presented to 4 decimal places; p-values less than 0.0001 will be presented as “<0.0001” and p-values greater than 0.9999 will be presented as “>0.9999”. All statistical output will be presented in statistical appendices where appropriate.

Analyses will be performed by dose arm for all efficacy, immunological, PK, PD and safety data, with the exception of adverse event (AE) data which will be presented by dose arm and overall (Section 13.6).

In the event that the number of planned infusions in the dose arms are modified following review by the DMC, the data will be summarized based on the actual dose arms completing the study. For example, if the 5x4 mg/kg QWK dose arm is modified such that some subjects receive only 4 infusions, then the data will be summarized separately for this new dose regimen.

In the TFLs the dose arms will be displayed as follows where applicable:

- UCB7665 5x4mg/kg
- UCB7665 3x7mg/kg
- UCB7665 2x10mg/kg
- UCB7665 1x15mg/kg
- UCB7665 1x20mg/kg

If additional dose arms are initiated during the study these will be displayed similarly. For example, if the 5x4 mg/kg QWK dose arm is modified such that some subjects receive only 4 infusions this dose arm will be displayed as UCB7665 4x4mg/kg QWK in the TFLs.

Data listings containing all documented data and all derived data will be generated.

3.2 General study level definitions

3.2.1 Analysis timepoints

3.2.1.1 Relative day

Relative day for an event will be derived with the date of the first infusion of UCB7665 as reference.

Relative days for an event of measurement occurring before the date of first infusion are calculated as follows:

$$\text{Relative Day} = [(\text{Event Date} - \text{Date of First Infusion})]$$

The relative day for an event or measurement occurring on or after the reference date to the date of the last infusion is calculated as follows:

$$\text{Relative Day} = [(\text{Event Date} - \text{Date of First Infusion}) + 1]$$

For events or measurements occurring after the date of the last infusion, relative day will be prefixed with '+' in the data listings and will be calculated as follows:

$$\text{Relative Day} = + [(\text{Event Date} - \text{Date of Last Infusion})]$$

There is no relative Day 0. Relative day is not calculated for partial dates in cases where relative day is shown in a subject data listing. In such cases, relative day should be presented as '-' in the subject data listings.

3.2.1.2 Study periods

For each subject the duration of the study is approximately 16 weeks.

- Screening Period: 1 to 28 days
- Dosing Period: 1 to 4 weeks; during the Dosing Period subjects will receive weekly doses of UCB7665 (5 doses of 4mg/kg [QWK] in Dose Arm 1, 3 doses of 7mg/kg [QWK] in Dose Arm 2, 2 doses of 10mg/kg [QWK] in Dose Arm 3, 1 dose of 15mg/kg in Dose Arm 4 and 1 dose of 20mg/kg in Dose Arm 5). The dose regimen may be adapted following review by the DMC
- Observation Period: 8 weeks; a visit will be scheduled 3 days after the final dose (or only dose administration for Dose Arms 4 and 5) and weekly thereafter to collect safety and efficacy data

The end of the study is defined as the date of the last visit of the last subject in the study.

3.3 Definition of Baseline values

Baseline will be the last available predose value prior to the first infusion of UCB7665, or if missing, the latest non missing value prior to Baseline (screening value or unscheduled visit value).

Measurement-specific Baseline timepoints (based on the scheduled or unscheduled measurements) are presented in [Table 3–1](#).

Table 3–1: Definition of Baseline

Measurement	Definition of Baseline

Safety data:
 
 Clinical chemistry (including proteins) Hematology (including platelets measured locally) Coagulation Urinalysis Vital signs 12-lead ECG Serum safety biomarkers [REDACTED] 	
 Predose Day 1 or if missing the latest non missing value prior to Day 1

Efficacy variables:
 
 Platelets (measured by ACM Global Central Laboratory) ITP bleeding scale NFI-MS 	
 Platelets: Predose Day 1 or if missing the latest non missing value prior to Day 1 ITP bleeding scale: Predose Day 1 or if missing the latest non missing value prior to Day 1 NFI-MS: Predose Day 1

Pharmacodynamic variables:
 
 Total IgG IgG subclasses ITP-specific autoantibodies in serum [REDACTED] 	
 Total IgG: Predose Day 1 or if missing the latest non missing value prior to Day 1 IgG subclasses: Predose Day 1 or if missing the latest non missing value prior to Day 1 ITP-specific autoantibodies: Predose Day 1

Immunological variables:
 
 Immunoglobulins (IgA, IgE and IgM) B- and T-lymphocytes Serum (C3 and C4) and plasma complement (C3a and C5a) ADA Serum BAFF Cytokines, if applicable (as outlined in the protocol) 	
 Predose Day 1 (except B- and T-lymphocytes) B- and T-lymphocytes: Predose Day 1 or if missing the latest non missing value prior to Day 1

ADA=anti-drug antibody; BAFF= B cell activating factor; ECG=electrocardiogram; Ig=immunoglobulin; ITP=primary immune thrombocytopenia; NFI-MS= Neurological Fatigue Index for Multiple Sclerosis; [REDACTED]

If a measurement is repeated at Baseline and is obtained prior to receiving the first dose of UCB7665, then the last available measurement will be used as the Baseline value.

For the platelet count performed at Screening (measured by ACM Global Central Laboratory only), 2 separate blood samples will be obtained on the same day. If the latest non missing value prior to Baseline is to be used as Baseline (i.e., predose Day 1 is missing), the highest value for the platelet count obtained from the last 2 non missing measurements prior to Baseline will be used as the Baseline.

3.4 Protocol deviations

Important protocol deviations are deviations from the protocol which potentially could have a meaningful impact on study conduct or on the primary efficacy, key safety, or PK/PD outcomes (if applicable) for an individual subject. The criteria for identifying such protocol deviations will be defined within the important protocol deviation specifications which is part of the data cleaning plan. Important protocol deviations will be reviewed as part of the ongoing data cleaning process and data evaluation. All important protocol deviations will be discussed and documented at the data evaluation meeting (DEM) together with any decisions regarding exclusion from analysis sets.

3.5 Analysis sets

3.5.1 Enrolled Set

The Enrolled Set (ES) will consist of all subjects who have given informed consent. This will include screening failures. Screening failures will be labeled as 'not treated' in any outputs based on the ES.

3.5.2 Safety Set

The Safety Set (SS) will consist of all subjects who have received at least 1 infusion (full or partial infusion) of UCB7665 and will be used for the analysis of safety data.

3.5.3 Full Analysis Set

The Full Analysis Set (FAS) will consist of all subjects who have received at least 1 infusion (full infusion) of UCB7665 and, in addition, have a Baseline and at least 1 post-Baseline measurement for platelet count (measured by ACM Global Central Laboratory).

The analysis of the PD (excluding total IgG and IgG subclasses), efficacy and immunologic variables will be performed on the FAS. Efficacy analyses will be repeated for the pharmacodynamics per protocol set (PD-PPS) where stated in the SAP.

Platelet data for subjects who have taken rescue medications (based on medical review and defined in Section 8.1.4) will only be utilized in the summary tables up to the start of these rescue medications.

3.5.4 Per Protocol Set

The Per Protocol Set (PPS) is a subset of the FAS, consisting of those subjects who had received all foreseen sc infusions, had a platelet count measurement (measured by ACM Global Central Laboratory) during the Observation Period, and no important protocol deviations that may potentially affect the platelet count as confirmed during a pre-analysis review of the data prior to database lock. Protocol deviations may not necessarily lead to total exclusion of a subject from the PPS but may lead to exclusion of specific data and/or timepoints from the analysis.

Platelet data for subjects who have taken prohibited medications potentially affecting platelet counts such as IV corticosteroids, TPO-Rs, Oral corticosteroids, immunosuppressants (based on medical review) will only be utilised in the summary tables, up to the start date of these prohibited medications.

3.5.5 Pharmacokinetic Per Protocol Set

The Pharmacokinetic Per Protocol Set (PK-PPS) is a subset of the FAS, consisting of those subjects who had no important protocol deviations potentially affecting the plasma concentration of UCB7665, as confirmed during a pre-analysis review of the data prior to database lock.

3.5.6 Pharmacodynamic Per Protocol Set

The Pharmacodynamic Per Protocol Set (PD-PPS) is a subset of the FAS, consisting of those subjects who had no important protocol deviations potentially affecting the serum concentration of total IgG, as confirmed during a pre-analysis review of the data prior to database lock. Protocol deviations may not necessarily lead to total exclusion of a subject from the PD-PPS but may lead to exclusion of specific data.

The PD-PPS will be used for the analysis of the total IgG and IgG subclasses.

3.6 Treatment assignment and treatment groups

Treatment (dose arm) assignment for the SS, FAS, PK-PPS, PD-PPS and the PPS will be according to the planned treatment regimen (reflecting the potential DMC decisions).

In the event that the number of planned infusions in the dose arms are modified following review by the DMC, the data will be summarized based on the actual dose arms completing the study. For example, if the weekly 5x4mg/kg QWK dose arm is modified such that some subjects receive only 4 infusions, then the data will be summarized separately for this new dose regimen.

Analyses will be performed by dose arm, unless otherwise stated.

3.7 Center pooling strategy

The clinical study will be conducted in multiple centers in Europe and Australia. The data from different sites will be pooled for all analyses. There will be no analyses by site or country performed.

3.8 Coding dictionaries

Adverse events and medical history will be coded using the latest available version of the Medical Dictionary for Regulatory Activities (MedDRA[®]).

Medications will be coded according to the World Health Organization Drug Dictionary (WHODD [September 2015]). Medical procedures will not be coded.

3.9 Changes to protocol-defined analyses

The protocol stated that changes from Baseline would be evaluated for the ITP-specific autoantibodies. However, as these data are semi-quantitative, changes from Baseline are not considered an appropriate way to present the results and would not provide any additional information. Thus, only absolute values over time will be reported.

4 STATISTICAL/ANALYTICAL ISSUES

4.1 Adjustments for covariates

There will be no adjustment for covariates.

4.2 Handling of dropouts or missing data

In general, there will be no imputation of missing data unless otherwise stated below.

4.2.1 Efficacy data

There will be no imputation of missing platelet data (measured by ACM Global Central Laboratory) or missing data for the ITP bleeding score. Missing data for the calculation of the NFI-MS summary score will be handled as described in [Section 13.2](#).

4.2.2 Safety laboratory data

Measurements below the limit of quantification (BLQ) will be imputed with half of the lower limit of quantification (LLOQ) for the purpose of calculating change from Baseline and for descriptive statistics. Measurements above the limit of quantification (ALQ), if applicable, will be imputed to the upper quantification limit.

These rules will be applied to all safety laboratory data including coagulation parameters, clinical chemistry and urinalysis.

4.2.3 Pharmacodynamic data

Measurements BLQ are not anticipated in the PD data (total IgG [measured by ACM Global Central Laboratory] and IgG subclasses). In the event that any BLQ measurements are received, these will be discussed at the DEM.

For the ITP-specific autoantibodies any measurements that are above the limit of detection (ALD) will be imputed with the value of the upper quantification limit for the calculation of summary statistics.

4.2.4 Immunological data

The rules for handling BLQ or ALQ measurements for all immunological data (including IgA, IgE, IgM, B- and T-lymphocytes, serum and plasma complement, serum biomarkers (including BAFF), ADA and cytokines) will be as described in [Section 4.2.2](#).

For all immunological data, measurements that are BLQ will be imputed with LLOQ/2 for individual plots.

4.2.5 UCB7665 concentration data

Measurements that are BLQ will be imputed with LLOQ/2 for the purpose of calculating the geoMean and its 95% CI, the geoCV, the arithmetic mean, and SD for summaries and figures.

For the individual figures, any concentrations that are BLQ will be imputed with LLOQ/2, with the exception of predose BLQ measurements on Day 1, which will be imputed with zero for linear scale plots.

Additional rules for PK data summaries are provided in [Section 9.1](#).

4.2.6 Electrocardiogram data

For the ECG data, all calculations of changes from Baseline and descriptive statistics will be based on the mean of the triplicate assessments at each visit. In the event that there are not 3 available measurements at a given visit, the mean will be calculated based on the number of measurements for which data is provided (variables analyzed will be those described in Section 10.4.2).

4.2.7 Dates and times

Partial dates may be imputed for the following reasons:

- Classification of AEs as treatment-emergent
- Classification of medications as past, prior or concomitant

Imputed dates will not be shown in the listings; all dates will be displayed as reported in the database.

The following rules will be applied for partial start dates:

- If only the month and year are specified and the month and year of first dosing is not the same as the month and year of the start date then use the 1st of the month, or the date of screening if this is later (if the latter imputation results in an end date that is earlier than the start date, then use the 1st of the month). If time is missing this will be imputed as 00:00 h;
- If only the month and year are specified and the month and year of first dosing is the same as the month and year of the start date, then use the date of first dosing. If this results in an imputed start date that is after the specified end date, then use the 1st of the month, or the date of screening if this is later (if the latter imputation results in an end date that is earlier than the start date, then use the 1st of the month). If the imputed date is the date of first dosing then time will be imputed as the start time of the infusion (i.e., event will be regarded as treatment-emergent);
- If only the year is specified, and the year of dosing is not the same as the year of the start date then use January 01 of the year of the start date. If time is missing this will be imputed as 00:00 h;
- If only the year is specified, and the year of dosing is the same as the year of the start date, then use the date of dosing. If this results in an imputed start date that is after the specified end date, then use January 01 of the year of start date, or the date of screening if this is later (if the latter imputation results in an end date that is earlier than the start date, then use January 01). If the imputed date is the date of first dosing then time will be imputed as the start time of the infusion (i.e., event will be regarded as treatment-emergent);
- If the start date is completely unknown, then use the date of first dosing. If this results in an imputed start date that is after the specified end date, then use January 01 of the year of the end date, or the date of screening if this is later (if the latter imputation results in an end date that is earlier than the start date, then use January 01). If the imputed date is the date of first dosing then time will be imputed as the start time of the infusion (i.e., event will be regarded as treatment-emergent).

Start and end time is not recorded for concomitant medications, thus no imputations for missing times will be performed. Any medication with a start date on the first dosing date, will be assumed to be concomitant.

The following rules will be applied for partial stop dates:

- If only the month and year are specified, then use the last day of the month;
- If only the year is specified, then use December 31 of the known year;
- If the stop date is completely unknown, do not impute the stop date, except for ITP medications where end date is missing and ongoing is ticked as ‘no’, which will be imputed as “Past” medications.

Missing or partially missing date and/or times will be imputed as described in [Table 4-1](#) for the calculation of duration of each AE. Adverse event duration is computed and reported in day and time format: xx d hh:mm.

Table 4-1: Calculation rules for duration of adverse events

Data availability	Onset date/time	Outcome date/time	Calculation rules
Complete data	D1/T1	D2/T2	Duration = $[(D2 - D1) * 24 + (T2 - T1)] / 24$ d
End time missing	D1/T1	D2/--	End time is substituted by time 23:59h (=23.98 in decimal format) Duration = $\langle [(D2 - D1) * 24 + (23.98 - T1)] / 24$ d
Start time missing	D1/--	D2/T2	Onset time is substituted by time 00:00h. Duration = $\langle [(D2 - D1) * 24 + T2] / 24$ d
Start and end time missing	D1/--	D2/--	Duration = $\langle D2 - D1 + 1$
Start day and time missing	--/--	D2/T2	Duration = $\langle [(D2 - D0) * 24 + (T2 - T0)] / 24$ d For a subject in the SS, D0 and T0 are the date and time of first administration of UCB7665 and for screen failures, D0 is the date of the screening visit and T0 = 00:00h
End day and time missing	D1/T1	--/--	For ongoing AE: Duration = \rangle Discharge day - D1 d For resolved AE: Duration = \langle Discharge day - D1 d Where discharge refers to the date of the end of study visit or the date of discontinuation for subjects that were withdrawn. For any AEs with known start date/time after the date of discontinuation, the date of last contact will be used as the discharge day.

Table 4–1: Calculation rules for duration of adverse events

Data availability	Onset date/time	Outcome date/time	Calculation rules
Start and end date missing	--/--	--/--	
For ongoing AE: Duration = >Discharge day – D0 d
 
For resolved AE: Duration = <Discharge day – D0 d
 
For a subject in the SS, D0 and T0 are the date and time of first administration of UCB7665 and for screen failures, D0 is the date of the screening visit and T0 = 00:00h.
 
Discharge refers to the date of the end of study visit or the date of discontinuation for subjects that were withdrawn.
 
For any AEs with known start date/time after the date of discontinuation, the date of last contact will be used as the discharge day.

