4.8 Examination of subgroups

The following subgroups will be defined within each dose arm:

- Concomitant corticosteroid medication: Yes/No

Concomitant medication is defined in Section 6.4.4. The list of applicable Anatomical Therapeutic Chemical (ATC) codes to be utilized as corticosteroids is provided in Section 13.1.

- Responder at the end of past ITP therapy: No/Yes/Unknown

Responder categories will be defined utilizing the value (either Yes or No) for the last reported ITP therapy for each patient. If this value is unknown, the second-last reported ITP therapy value will be used, then the third-last, and so on, until a known response is provided. The Unknown responder category will only be considered in cases where the investigator has never reported a category (Yes or No) for any of the past ITP therapies. For the 'Response' definition, the CRF entries will be utilized.

The past ITP therapy is defined as procedure history related to ITP or past medication related to ITP, where past medication is defined in Section 6.4.1. For 'related to ITP' CRF entries will be utilized.

The corticosteroid medication given more than 3 months prior to screening was routinely not recorded and cannot be considered. Thus, some patients with an unknown response might have had a known response.

- Past intravenous immunoglobulin (IVIg) medication: Yes/No

Past medication is defined in Section 6.4.1. The ATC Therapeutic Subgroup code (Level 2) 'IMMUNE SERA AND IMMUNOGLOBULINS' will be utilized.

- Number of past ITP therapies: $\leq 2 / > 2$

The past ITP therapy is defined as procedure history related to ITP or past medication related to ITP, where past medication is defined in Section 6.4.1. For ‘related to ITP’ CRF entries will be utilized.

The corticosteroid medication given more than 3 months prior to screening was routinely not recorded and cannot be considered. Thus, some patients might have had 1 more past ITP therapy than utilized for subgroup determination.

The descriptive summaries for platelets and total IgG will be presented for the subgroups above.

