6.4.1 Past medication definition

Past medications will include any medications that started and stopped prior to the first administration of UCB7665.

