6.4.4 Concomitant medication definition

Concomitant medications will include any medication that has been taken at least once (after the first administration of UCB7665) during the Dosing Period and/or the Observation Period.

This includes medications that started prior to the dosing and continued after (classified as prior and concomitant medications) as well as any medication that started after the first administration of UCB7665 (classified as concomitant).

Any medications with missing dates and/or times will be handled as described in [Section 4.2.7](#) in order to classify them as prior and/or concomitant.

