8.1.4 Rescue medication definition (after medical inspection)

In the rescue medication section of the protocol, rescue medication is defined as platelet substitution or treatment with a commercially available IVIg. In addition, the prohibited medications PLEX, dexamethasone and rituximab will also be considered as a rescue medication for analysis.

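### Section 4.2.7 classes ITP medications with no end date and ongoing ticked no as Past, even when they started on or after the first infusion

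*SAP*

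**What the plan says.** Section 4.2.7 allows partial dates to be imputed for, among other things, "Classification of medications as past, prior or concomitant". Its general rule for end dates is "If the stop date is completely unknown, do not impute the stop date". One exception follows, "except for ITP medications where end date is missing and ongoing is ticked as" no: these records become Past. Nothing in the sentence refers to the start date.

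The classes themselves are defined in section 6.4. Under 6.4.1, "Past medications will include any medications that started and stopped prior to the first administration of UCB7665". Under 6.4.4, "Concomitant medications will include any medication that has been taken at least once (after the first administration of UCB7665"), and this expressly takes in "any medication that started after the first administration of UCB7665 (classified as concomitant"). Section 6.4.4 then refers records with missing dates back to 4.2.7.

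Section 4.2.7 has two further rules that matter here. A medication starting on the first dosing date is taken to be concomitant, and a completely unknown start date is set to the first dosing date.

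**The concern.** The exception overrides the definition of the class into which it puts records. Past is meant for treatment that was over before the first infusion. As written, an ITP drug begun during the Observation Period goes into that class if the site leaves the end date blank and marks the drug as not ongoing.

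The split between past and concomitant matters most for ITP therapies, because it defines subgroups in section 4.8. A treatment started after baseline, possibly because of how the subject was doing on study drug, would then help to define what is presented as a pre-treatment characteristic. It would also be missing from the table in which a reader looks for treatment given alongside UCB7665.

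**Working it through.** No figure in the plan is at issue, so the check sets the rules side by side. Take an ITP medication with a completely missing end date and ongoing ticked no, and vary only the start date.

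| Start date | Class under the other rules | Class under the exception | Result |
|---|---|---|---|
| Recorded, after first infusion | Concomitant (6.4.4); cannot meet 6.4.1 | Past | Contradiction |
| Recorded, on first dosing date | Concomitant (4.2.7) | Past | Contradiction within 4.2.7 |
| Wholly unknown | Imputed to first dosing date, so concomitant (4.2.7) | Past | Contradiction within 4.2.7 |
| Recorded, before first infusion | Past, or prior and concomitant, depending on the true stop | Past | Possible, not established |

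Three of the four cases conflict with another rule in force. Three details support this reading.

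1. Section 6.4.4 sends missing dates to 4.2.7, so the general definitions do not override the exception.
2. The unknown-start rule moves the imputed date back only when it falls after a specified end date. Here there is no end date, so the imputed start stays at first dosing. The same holds for a partial start in the month and year of first dosing.
3. In the fourth case, ongoing ticked no shows that the drug has stopped, not that it stopped before the first infusion.

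A post-dose record filed as Past then travels as follows.

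- Medication tables (6.4): it leaves the concomitant table and enters Past. It also enters Prior, because 6.4.2 includes past medications, and so can reach the table of prior ITP medications in 6.2.
- Number of past ITP therapies (4.8): it adds one. The subgroup changes only if the count moves from 2 to 3.
- Past IVIg (4.8): an immunoglobulin record turns No into Yes only if the subject has no other past record of that class.
- Responder at the end of past ITP therapy (4.8): it matters if the record becomes the last reported therapy with a known response.
- "Concomitant corticosteroid medication: Yes/No" (4.8): an ITP corticosteroid record turns Yes into No only if the subject has no other concomitant corticosteroid.

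These subgroups are used for the platelet summaries (8.1.2), responder rates (8.1.3.3) and total IgG (9.2.2). Past IVIg and the past-therapy count are also used for Clinical Response (8.2.1.1).

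**The case against.** The strongest reply is that the defect is narrow and mostly visible. The exception applies only when day, month and year of the end date are all missing; a partial end date is imputed to the end of its month or year. An in-study drug with no end date at all, yet marked as stopped, should be uncommon. The rule came in with SAP Amendment 3 and may have been aimed at treatment-history entries. All medications are listed with dates as reported, so a post-dose start labelled Past could be seen. The subgroup outputs are descriptive, with no test attached. All of this stands and limits the weight of the point. It does not remove the contradiction, because the text does not confine the rule to history entries and a programmer would code it as written.

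Three stronger readings are tempting, and the SAP does not support them.

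- A reader might infer that rescue treatment hidden as Past leaves rescue-driven counts in the platelet and IgG tables and creates false responders. Section 8.1.4 says that "rescue medication is defined as platelet substitution or treatment with a commercially available IVIg", adds certain prohibited drugs, and by its heading rests on medical inspection. Sections 3.5.3, 8.1, 8.1.3.3 and 9.2.2 cut the data at the start of the rescue medication; 3.5.4 does the same for prohibited medication in the PPS. A Past label changes neither the start date nor the review. What remains open is a rescue-type drug with an unknown start: imputation would put it at first dosing, while Past implies a pre-study drug.
- A reader might size the effect as one subject in an arm of 15 to 6, that is 1/15 = 6.7% to 1/6 = 16.7%. This is a share of the arm, not the shift in a subgroup cell. Cell sizes are not given.
- A reader might infer that every other drug with an unknown stop date stays concomitant. The SAP says only that its stop date is not imputed.

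**Conclusion.** The point holds as a rule that assigns the wrong class. For a recorded start on or after the first infusion, the exception contradicts 6.4.1, 6.4.4 or 4.2.7 itself. For a wholly unknown start, 4.2.7 gives two answers. The effect falls on the medication tables and, subject to the conditions in the working, on descriptive subgroup labels. Its size cannot be stated, because the number of such records is not in the document; that it is small is a judgement based on the narrow trigger. Rescue truncation and responder status are not affected when the start date is known. The wording should still be corrected, since the correction is cheap and the affected drugs are those for which the class matters most.

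**What to change.** In section 4.2.7:

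1. Restrict the exception to ITP medications whose recorded start date, or its known part, is before the first infusion.
2. State that an ITP medication with a recorded start on or after the first infusion is concomitant whatever its stop date.
3. State which rule prevails when the start is wholly unknown. One option is Past if the record was entered as ITP treatment history, and concomitant otherwise. Without this, the start-date rule would file undated historical therapy as in-study treatment.
4. Flag pre-dose starts with an unknown stop date for review at the data evaluation meeting. The start-date condition alone would leave a background ITP drug stopped during the study still classed as Past.

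No change to the rescue cut-off rule is needed where the start date is known. The cost is a few sentences and one extra condition in the derivation. The small downside is that a few undated records need case review.
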